DSMB	Data Safety Monitoring Board
EU	European Union
EudraCT	European drug regulatory affairs Clinical Trials
GCP	Good Clinical Practice
GDPR	General Data Protection Regulation; in Dutch: Algemene Verordening Gegevensbescherming (AVG)
IB	Investigator's Brochure
IC	Informed Consent
IMP	Investigational Medicinal Product
IMPD	Investigational Medicinal Product Dossier
METC	Medical research ethics committee (MREC); in Dutch: medisch-ethische toetsingscommissie (METC)
(S)AE	(Serious) Adverse Event
SPC	Summary of Product Characteristics; in Dutch: officiële productinformatie IB1-tekst
Sponsor	The sponsor is the party that commissions the organisation or performance of the research, for example a pharmaceutical company, academic hospital, scientific organisation or investigator. A party that provides funding for a study but does not commission it is not regarded as the sponsor, but referred to as a subsidising party.
SUSAR	Suspected Unexpected Serious Adverse Reaction

- UAVG** Dutch Act on Implementation of the General Data Protection Regulation; in Dutch: Uitvoeringswet AVG
- WMO** Medical Research Involving Human Subjects Act; in Dutch: Wet Medisch-wetenschappelijk Onderzoek met Mensen

SUMMARY

Rationale: Gastrointestinal malignancies are rare in children and adolescents. Consequently, data on clinical features, treatments and outcomes of these patients are limited.

Objective: We aim to describe the patient and tumor characteristics, treatments, and outcomes of children and adolescents diagnosed with primary gastrointestinal malignancies, and to analyze these data for trends over time. In addition, we want to explore independent prognostic factors for overall survival. Finally, we want to describe subsequent primary malignancies diagnosed among patients from the study cohort, as well as to calculate their risk of developing a second primary cancer relative to the general population. Data on children (aged 0-17 years at diagnosis) and young people aged 18-24 years at diagnosis are analyzed separately. Special focus is laid on patients with primary carcinomas of the gastrointestinal tract; particularly colorectal carcinoma.

Study design: This is an observational population-based cohort study based on the publicly available Surveillance, Epidemiology, and End Results (SEER) database.

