2. OBJECTIVES

Primary Objective: To describe the patient and tumor characteristics, first course treatments, survival and subsequent primary malignancies of children and adolescents diagnosed with primary gastrointestinal malignancies.

Secondary Objective(s): 1) To investigate time trends in incidence, stage at diagnosis, first course treatments, mortality, and overall survival. 2) To explore independent prognostic factors for overall survival. 3) To calculate the standardized incidence of second primary malignancies in childhood and adolescent gastrointestinal cancer survivors, relative to the general population.

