EOD 10 - size (1988-2003)	Extent of Disease - Historic
Months from diagnosis to treatment	Therapy
RX Summ--Surg Prim Site (1998+)	Therapy
Reason no cancer-directed surgery	Therapy
Radiation recode	Therapy
Chemotherapy recode (yes, no/unk)	Therapy
B Symptoms Recode (2010+)	Site-Specific Data Items
CEA Pretreatment Interpretation Recode (2010+)	Site-Specific Data Items
Survival months	Cause of Death (COD) and Follow-up
Survival months flag	Cause of Death (COD) and Follow-up
Vital status recode (study cutoff used)	Cause of Death (COD) and Follow-up
COD to site recode	Cause of Death (COD) and Follow-up
SEER cause-specific death classification	Cause of Death (COD) and Follow-up
SEER other cause of death classification	Cause of Death (COD) and Follow-up

Patients are categorized into two age groups: children (aged 0-17 years at diagnosis) and young people aged 18-24 years at primary gastrointestinal cancer diagnosis. In principle, data is analyzed and presented by 1-year age category or by age group (<18 or 18-24 years at diagnosis), except for age distributions of specific patient populations (e.g. patients with colorectal carcinoma). When data from children and young people aged 18-24 years are analyzed together, then this is clearly stated in the accompanying text. Race is categorized into White, Black, and Other. Origin is categorized into Hispanic and non-Hispanic. Together, race and origin are reported in

Legend Table 2. Abbreviation: NOS, not otherwise specified. Symbols: * Contrary to the Rare Cancer Classification, cancers with ICD-O-3 morphology codes 8000-8009 ("neoplasms, NOS") and ICD-O-3 topography codes C015-C026 ("digestive organs") are not classified (e.g. morphology code 8002 as NEN; morphology codes 8000-8001 and 8003-8005 as epithelial tumors). Instead, these cancers are grouped within "rare other and unknown subtypes" in our study. This decision is made because – in our study population – the likelihood that digestive cancers of unspecified histologic subtype are of neuroendocrine or epithelial origin is not necessarily highest. In our young patient population, malignancies in these anatomic locations are relatively often other cancers, such as lymphomas, sarcomas or blastomas.

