8.1.2 Secondary study parameters/endpoints

1. Time trends in incidence, stage at diagnosis, first course treatments, mortality, and overall survival.
2. Associations between the variables age at diagnosis, sex, race and origin, year of diagnosis, stage at diagnosis, and histologic category (when relevant) with overall survival in multivariable analysis.
3. Standardized incidence of second primary malignancies in patients who survived (i) two or more months, or (ii) five or more years after gastrointestinal cancer diagnosis, relative to the general U.S. population.

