10.2 Secondary study parameter(s)

Data will be presented quantitatively (numerically); stratified by age group (<18; 18-24 years at diagnosis).

Age-adjusted incidence and mortality rates are calculated as the average annual number of cases or deaths per million person-years at risk, respectively. For mortality rates, calendar year and age (<18; 18-24 years) represent year and age at death, respectively. Incidence rates of the common gastrointestinal malignancies are based on SEER 17 incidence data (2000-2019); mortality rates of malignant neoplasms of the digestive organs (ICD-O-3 topography codes C015-C026) are based on mortality data of the total U.S. population (1969-2019). In addition, incidence-based mortality (IBM) rates – for cases registered in SEER 17 – may be calculated to partition mortality by digestive cancer subtype (BL, UESL, NEN, HCC, HB, GC, and CRC)³³. The annual population size is obtained from the Census Bureau. Rates are age-standardized using the age structure of the 2000 U.S. standard population. Rates are calculated using SEER*Stat software and plotted using 3-year moving averages³⁴. When 3-year moving averages vary greatly, rates may be plotted using 5- or 7-year moving averages. Trends over time in incidence and mortality are analyzed by Poisson regression, with the calendar year as a continuous regressor variable. In addition, trends over time may be evaluated by linear regression modelling – a method frequently used in prior studies^{34,35} – to allow easier comparisons between studies, as well as with Jointpoint regression modelling to identify change points in the trends. Results are reported as average annual percent changes (AAPC) along with 95% confidence intervals and *P* values.

Trends over time in stage at diagnosis or first course treatments of patients with common GI malignancies are tested with logistic regression, with year of diagnosis as a continuous variable³⁴. The proportions of each stage at diagnosis or treatment category are plotted as weighted 3-year moving averages in percentages. When weighted 3-year moving averages vary greatly, results may be plotted using weighted 5- or 7-year moving averages.

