Standardized incidence ratios (SIR) and 95% confidence intervals of second primary malignancies (SPM) in patients that survived i) two or more months, or ii) five or more years after initial gastrointestinal cancer diagnosis are estimated using the multiple primary (MP-SIR) session of SEER*Stat software. Analyses are performed by common gastrointestinal cancer subgroup (BL, UESL, NEN, HCC, HB, GC, and CRC). SIR calculations compare the observed second cancer incidence with the expected first primary cancer incidence in the age-, sex-, race- and calendar year-matched general population²⁹. The general population rates are available by cancer site, 5-year age categories, sex, race and 5-year diagnostic time periods.

A *P* value < 0.05 is considered statistically significant.

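### Section 10.2 names second-cancer SIRs only by seven common cancers, so secondary objective 3, which concerns GI cancer survivors as a cohort, has no cohort-level SIR

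*Combined protocol and SAP*

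**What the plan says.** **Target.** Section 2 gives secondary objective 3 as "To calculate the standardized incidence of second primary malignancies in childhood and adolescent gastrointestinal cancer survivors, relative to the general population". The Summary says that the investigators will "calculate their risk of developing a second primary cancer relative to the general population", where the pronoun refers to patients from the study cohort. The endpoint in section 8.1.2 is "Standardized incidence of second primary malignancies in patients who survived (i) two or more months, or (ii) five or more years after gastrointestinal cancer diagnosis". None of the three limits the target to particular GI cancers. Section 4.2 admits every malignant first primary of the digestive organs, and the legend to Table 2 in section 8 shows that the cohort holds a group of "rare other and unknown subtypes".

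**Planned analysis.** In section 10.2, SIRs for the two survivor sets "after initial gastrointestinal cancer diagnosis are estimated using the multiple primary (MP-SIR) session of SEER*Stat software". The next sentence sets the unit of analysis: "Analyses are performed by common gastrointestinal cancer subgroup (BL, UESL, NEN, HCC, HB, GC, and CRC"). The section opens with a default age split: "Data will be presented quantitatively (numerically); stratified by age group (<18; 18-24 years at diagnosis"). Section 8 allows an exception: "When data from children and young people aged 18-24 years are analyzed together, then this is clearly stated in the accompanying text". No pooling of ages is declared for the SIR.

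**The concern.** The objective and the endpoint are worded for a cohort, but the only unit of analysis named for the SIR is the individual common cancer. Two things follow if the text is carried out literally.

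- No estimate compares second-cancer incidence in GI cancer survivors as a group with the general population, although that is how the objective is phrased.
- Survivors whose first GI cancer is outside the seven contribute neither person-years nor second cancers to any SIR.

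The information on a rare outcome in rare cancers is also divided among many cells. Some may hold very few second cancers or none, and no pooled figure is planned to set beside them.

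**Working it through.** The plan gives no sample size, expected count or event number for the SIR (section 4.4 gives the descriptive primary objective as the reason for having no sample size), so there is no figure of its own to reproduce. The check is a comparison of the text, a count, and an illustration of precision.

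**1. Target against analysis**

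| Place | Population for the SIR |
|---|---|
| Summary; section 2; section 8.1.2 | GI cancer survivors, no restriction by type |
| Section 4.2 | all malignant first primaries of the digestive organs |
| Section 10.2, first SIR sentence | survivors of an initial GI cancer, no restriction by type |
| Section 10.2, second SIR sentence | BL, UESL, NEN, HCC, HB, GC, CRC |

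No all-GI row and no row for the remaining types is named. By contrast, the same section plans mortality for the digestive organs as a whole and then offers incidence-based mortality to divide it by the same seven types. For the SIR, only the division is named.

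**2. Number of SIRs**, counting one per cell for all second cancers together

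- Default age split: 7 cancers x 2 age groups x 2 survivor sets = 28.
- Ages pooled and declared: 7 x 2 = 14.
- Whole cohort: 0 in either case.

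**3. Precision for a given number of observed second cancers, O**

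The exact Poisson 95% limits for the count are chi-square(0.025; 2O)/2 and chi-square(0.975; 2O + 2)/2. Dividing by O expresses them as multiples of the estimated SIR.

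| O | Limits for the count | Multiples of the SIR |
|---|---|---|
| 0 | upper 3.69 | upper limit only: 3.69 / expected count |
| 1 | 0.025 to 5.57 | 0.03 to 5.6 |
| 2 | 0.24 to 7.22 | 0.12 to 3.6 |
| 3 | 0.62 to 8.77 | 0.21 to 2.9 |
| 28 (14 cells x 2) | 18.6 to 40.5 | 0.66 to 1.45 |

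**4. Chance of detecting a raised risk, over a range of assumptions**

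Assume a pooled expected count E in one survivor set, split evenly over 7 x 2 = 14 cells, with an exact Poisson test whose upper tail is 0.025. Power is P(X >= c) for X ~ Poisson(E x SIR), where c is the smallest count with upper-tail probability at most 0.025 under Poisson(E).

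| Assumed pooled E | True SIR | Pooled | One age group (E/2) | One cancer, ages combined (E/7) | One cancer and age group (E/14) |
|---|---|---|---|---|---|
| 5 | 2 | 42% | 24% | 6% | 4% |
| 5 | 3 | 88% | 62% | 17% | 9% |
| 10 | 2 | 70% | 42% | 16% | 6% |
| 10 | 3 | 99% | 88% | 43% | 17% |
| 20 | 2 | 96% | 70% | 22% | 16% |
| 20 | 3 | >99% | 99% | 62% | 43% |

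The counts in steps 3 and 4 are assumptions. Real cells will be uneven, and the illustration leaves out the types outside the seven.

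**The case against.** The best defence is that the plan is built this way throughout. Section 8 announces seven cancers for subgroup analysis. Secondary objective 2 is worded just as generally, yet its Cox models in Table 4 cover the same seven. SIRs in seven groups of GI cancer survivors are still evidence on second-cancer risk in such survivors. Section 1 links that risk to genetic predisposition and to specific treatments, so it may well differ by first cancer. A pooled value would depend on case mix and could hide a high risk in one group. This argument stands against making a pooled SIR the main estimate. It does not supply the cohort-level comparison, and it leaves the remaining types unassessed.

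The wording is also open. Section 10.2 does not say that subgroup SIRs are the only ones, and its first SIR sentence could be read as an overall estimate that is then broken down. That too stands. But no overall row is named, and if one is intended, saying so is the same one-line change.

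A reader might infer more than the documents support:

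- **That 28 SIRs are fixed.** The figure is a ceiling. Section 1 makes the age split a preference, and section 8 permits declared pooling.
- **That the other cancer types vanish from the study.** They drop out of the SIR only. Section 10 describes subsequent malignancies across the cohort, though a description is not a comparison with the general population.
- **That all pancreatic tumours fall outside the seven.** The NEN row of Table 3 spans every digestive-organ topography code, so pancreatic neuroendocrine neoplasms are inside.

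**Conclusion.** The point holds as a mismatch between a stated secondary objective and the analysis named for it. As written, section 10.2 yields up to 28 subgroup SIRs, no cohort-level SIR, and no SIR to which survivors outside the seven contribute. The documents give no counts by cancer type, so the share of the cohort affected is unknown and could be small or large.

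The gain in precision from pooling is certain in direction but not in size: the limits of 0.12 to 3.6 times the SIR (2 events) against 0.66 to 1.45 times (28 events) rest on assumed counts. The planned 95% intervals would show the imprecision of any sparse subgroup.

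It would go too far to say that objective 3 is left wholly unanswered or that the subgroup SIRs are the wrong analysis. They address part of the objective, and the documents give no ground for ranking them below a pooled value.

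**What to change.** Add to the SIR paragraph of section 10.2 an SIR for the whole cohort, covering all included GI malignancies and so also the types outside the seven. Estimate it for each of the two survivor sets, by age group and with ages combined, labelling the combined result as section 8 requires. That adds 2 survivor sets x 3 (two age groups and combined) = 6 SIRs. Report them beside the seven subgroup SIRs, with neither ranked below the other, and give observed and expected counts for every SIR.

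The cost is one sentence and one more run of the same MP-SIR session. The small downside is that the pooled SIR averages over cancers that may differ in second-cancer risk and depends on case mix, so the text should say that it is to be read together with the subgroup SIRs.

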10.3 Other study parameters

Not applicable

10.4 Interim analysis (if applicable)

Not applicable

11. ETHICAL CONSIDERATIONS

11.1 Regulation statement

In analogy to studies based on data from the Netherlands Cancer Registry³⁴, this observational study of anonymous data does not require approval from an ethics committee in the Netherlands, according to the Central Committee on Research involving Human Subjects (CCMO).

11.2 Recruitment and consent

Not applicable

11.3 Objection by minors or incapacitated subjects (if applicable)

Not applicable

11.4 Benefits and risks assessment, group relatedness

No risk or benefits

11.5 Compensation for injury

Not applicable

11.6 Incentives (if applicable)

Not applicable

12. ADMINISTRATIVE ASPECTS, MONITORING AND PUBLICATION

12.1 Handling and storage of data and documents

Retrieved data are anonymous. Access to SEER Research Plus data is provided under the SEER Research Data Use Agreement (<https://seer.cancer.gov/data-software/documentation/seerstat/nov2021/seer-dua-nov2021.html>). Data are available in SEER*Stat software. Exported data are stored on a secured network drive with regular back-ups.

12.2 Monitoring and Quality Assurance

No monitoring will take place.

12.3 Amendments

Amendments will be recorded and filed by the investigators.

12.4 Annual progress report

No progress report will be made.

12.5 Temporary halt and (prematurely) end of study report

Not applicable

12.6 Public disclosure and publication policy

The investigators are committed to publishing the results of the study in an international medical scientific journal; preferably open access. All investigators (including the study statistician) are co-author of the manuscript, following ICMJE guidelines.

13.STRUCTURED RISK ANALYSIS

Not applicable

13.1 Potential issues of concern

Not applicable

13.2 Synthesis

Not applicable

